8.0 Drugs and Devices

8.1 * DRUGS AND/OR BIOLOGICS: Are you **STUDYING** any drugs and/or biologics that are either approved or unapproved: **(REQUIRED)**

☐ Yes ☒ No

Note: This question is frequently answered incorrectly. If any drugs or biologics, approved or unapproved, are being administered under this protocol, you should check 'Yes' unless you are *absolutely* sure that **NONE** of the drugs are part of the research protocol. Tip: Ask the PI or the sponsor if you are not sure how to answer this question.

8.3 * MEDICAL DEVICES: Are you **STUDYING** any medical devices, in vitro diagnostics, or assays that are either approved or unapproved: **(REQUIRED)**

☒ Yes ☐ No

8.4 * NSR: Are you requesting a Non-Significant Risk (NSR) determination for an investigational device: **(REQUIRED)** Note: an **NSR determination** is different from an Investigational Device Exemption (IDE). Check the Help link for more guidance on what types of devices can qualify for an NSR determination.

☐ Yes ☒ No

8.5 LIST THE DEVICES: List the medical devices or in vitro diagnostics to be studied or used. In the device details screen you will be asked questions such as:

- Whether the device is FDA approved or investigational
- Medicare device category
- If the device will be provided at no cost
- If an IDE is necessary, the IDE number, and who holds the IDE
- Risk category of the device
- FDA status of the device

Please see the [UCSF IRB website](#) for more details about the use of devices in research, including the [Investigator Checklist for Significant Risk, Non-Significant Risk, and/or IDE Exempt Device Studies](#)
Verification of IDE numbers: If the sponsor's protocol does not list the IDE number, you must submit documentation from the sponsor or FDA identifying the IDE number for this study. Attach this documentation in the Other Study Documents section of the Initial Review Submission Packet. **If you have any correspondence from the FDA or sponsor regarding this device, please attach it to the application.**

View Details	Device Name	Is the Device FDA Approved	Is this a new device or a new use of an already approved device	IDE Number
	Delfi Personalized Tourniquet System	Yes	No	
Manufacturer/Supplier of Device		Delfi Medical Innovations Inc.		
Medicare Category		 A  B		
Where will the Devices Be Stored		UCSF Physical Therapy Centers		
Will Devices be supplied at no Cost		Yes		

Is this a HUD (HDE)	No
HDE Number	
Is the Device FDA Approved	Yes
Is this a new device or a new use of an already approved device	No
Is an IDE necessary	No
IDE Number	
Who holds the IDE	N/A
IDE details	
In the opinion of the sponsor, select the level of risk associated with this device	No Significant Risk

	SAGA Blood Flow Restriction Bands	No	Yes	
--------------------------	-----------------------------------	----	-----	--

Manufacturer/Supplier of Device	SAGA Fitness
Medicare Category	 A  B
Where will the Devices Be Stored	UCSF Physical Therapy Clinics
Will Devices be supplied at no Cost	Yes
Is this a HUD (HDE)	No
HDE Number	
Is the Device FDA Approved	No
Is this a new device or a new use of an already approved device	Yes
Is an IDE necessary	No
IDE Number	
Who holds the IDE	N/A
IDE details	
In the opinion of the sponsor, select the level of risk associated with this device	No Significant Risk

8.6 * EXPANDED ACCESS: Is this an expanded access or compassionate use protocol, meaning the primary purpose is to diagnose, monitor or treat a patient's condition, rather than the collection of safety and efficacy data of the experimental agent: (REQUIRED)

☐ Yes ☒ No

9.0 Sample Size and Eligibility Criteria

9.1 ENROLLMENT TARGET: How many people will you enroll:

105

If there are multiple participant groups, indicate how many people will be in each group:

Our goal enrollment is **105 patients total (35 per group in the randomized control trial and an additional 35 for the non-randomized group).**

9.3 SAMPLE SIZE JUSTIFICATION: Explain how and why the number of people was chosen. For multi-site studies, this is referring to the number that will be enrolled across all sites:

Power Analysis:

Aim 1 – Knee Extension

In a previously published study by Bowman et al., knee extension torque in this RCT's BFR group increased by 11% +/- 13 and the knee extension torque in the control group increased by 3% +/- 9 [5]. Using this data, the effect size expected is 0.72. Utilizing a goal of 0.8 power, alpha 0.05, and equal enrollment between groups, power analysis reveals a sample size goal of 50 patients (25 per group) for patients following meniscus repairs and 25 patients with additional orthopaedic knee conditions.

Aim 2 – Y-balance testing & IKDC

In Hughes et al. recent study comparing BFR to traditional heavy load resistance training in post-surgery ACL patients, Y-balance testing was most similar in the anterior direction, with scores normalized to leg length 32.9 +/- 9.7 for the BFR group and 17.5 +/- 6.7 in the traditional group [26]. Using this data, the effect size expected is 2.23. Utilizing a goal of 0.8 power, alpha 0.05, and equal enrollment between groups, power analysis reveals a sample size goal of 8 patients (4 per group) for Y-balance testing. For IKDC, overall mean difference in that paper was 35.63 +/- 7.06 for the BFR group and 23.33 +/- 8.76 for the traditional group [26]. The effect size with this data is 1.54. Utilizing a goal of 0.8 power, alpha 0.05, and equal enrollment between groups, power analysis reveals a sample size goal of 14 total patients for IKDC (7 per group). Of note, Irrgang et al. described the international knee documentation committee (IKDC) subjective knee form and determined the value for a true change in score of 9.0 points which was achieved in that study [27].

Overall, the power analysis is most limited by knee extension (75 total patients or 25 per group). To account for dropout, canceled surgeries, and patients who are unable to make all of their physical therapy visits, we aim to enroll 40% more, or a goal of **105 patients total (35 per group).**

9.4 * PARTICIPANT AGE RANGE: Eligible age ranges: (REQUIRED)

- ☐ 0-6 years
- ☐ 7-12 years
- ☐ 13-17 years
- ☒ 18-64 years
- ☐ 65+

9.5 * STUDY POPULATIONS: Data will be collected from or about the following types of people (check all that apply): (REQUIRED)

- ☐ Inpatients
- ☒ Outpatients
- ☐ Family members or caregivers
- ☐ Providers
- ☐ People who have a condition but who are not being seen as patients
- ☐ Healthy volunteers
- ☐ Students
- ☐ Staff of UCSF or affiliated institutions
- ☐ None of the above

9.6 * SPECIAL SUBJECT GROUPS: Check the populations that may be enrolled: (REQUIRED)

- ☐ Children / Minors
- ☐ Adult subjects unable to consent for themselves
- ☐ Adult subjects unable to consent for themselves (emergency setting)
- ☐ Subjects with diminished capacity to consent
- ☐ Subjects unable to read, speak or understand English
- ☐ Pregnant women
- ☐ Fetuses
- ☐ Neonates
- ☐ Prisoners
- ☐ Economically or educationally disadvantaged persons
- ☒ None of the above

9.7 INCLUSION CRITERIA: Briefly describe the population(s) that will be involved in this study. Include anyone that data will be collected from or about (e.g. patients, healthy controls, caregivers, providers, administrators, students, parents, family members, etc.):

Male and female patients, ages 18 to 60 years old, who are either: 1) undergoing arthroscopic meniscus repair of either the medial or lateral meniscus, or both. We will include all meniscus repair types (all-inside, inside-out, outside-in). 2) have an orthopedic knee condition, including but not limited to knee osteoarthritis, patellofemoral pain, and status post knee arthroscopy

9.8 EXCLUSION CRITERIA: List any exclusion criteria (e.g. reasons why someone would not be included in the study):

- Patients will be excluded if they have risk factors for venous thromboembolism, including cancer, currently on oral contraceptive medications, or prior history of thromboembolism.
- Additional exclusion diseases include sickle cell anemia, Diabetes Mellitus, and vascular disease for increased risk for vascular complications.

Increased risk for vascular complications will be listed as those with hereditary coagulopathies; or evidence of peripheral vascular disease on physical examination, including diminished pulses, skin changes, or history of lower extremity cramping pain with walking. History of venous thromboembolism will exclude a patient from the study.

9.9 * RESEARCH CONDUCTED ON PATIENT CARE WARDS: Do any study activities take place on any patient care units including inpatient wards, peri- or post-operative care units, operating rooms, or in the Emergency Department at UCSF Health medical facilities: (REQUIRED)

☒ Yes ☐ No

9.11 * EMERGENCY DEPARTMENT: Does your protocol or study involve any of the following patient related activities in the emergency department (e.g. subject identification, recruitment, consent, blood draws, specimen retrieval, involvement of ED staff (nursing, tech, and/or physician), or any other ED based procedures): (REQUIRED)

☐ Yes ☒ No

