3.5 If applicable, please select the Designated Department Approval(s)		
Add the name of the individual authorized to approve and sign off on this protocol from your Department (e.g. the Department Chair or Dean).		

4.0

Initial Screening Questions

Updated January 2019 - Revised Common Rule (January 2018) Compliant - v92

4.1 * PROJECT SUMMARY: (REQUIRED) Give a brief overview of this project (250 words or less). Tell us

what this study is about, who is being studied, and what it aims to achieve. If you have an NIH Abstract, paste it here (Click on the orange question mark to the right for more detailed instructions):

It is important to study innovative ways to enhance the rehabilitation of orthopaedic patients to optimally restore patient function. Blood flow restriction (BFR) is a training tool that has been shown to be useful in the rehabilitative setting, but its effectiveness in treating patients with orthopaedic knee conditions requires further investigation. This study therefore seeks to understand whether BFR is a useful rehabilitation tool across various populations with musculoskeletal knee conditions. BFR is a unique and promising strategy for patients who cannot tolerate high-load resistance training, as it can be combined with low-load exercises during rehabilitation to optimize muscle strength and hypertrophy. Patients that may benefit most from this are post-operative knee patients during early phases, including those that may have weightbearing restrictions, and patients with orthopaedic knee joint conditions with impaired load-tolerance. These patients must often limit physical activities due to post-operative surgical precautions or pain, which results in poorer patient outcomes, including muscular atrophy, increased risk of injury, and delayed return to activity/sports. This study will help clarify whether BFR can reduce these complications through improvements in strength, muscle size, and function in patients with orthopaedic knee conditions. If successful, this concept could be applied across other surgeries and disciplines within orthopaedics.

4.2 * HUD DEVICE: (REQUIRED) Does this application involve a Humanitarian Use Device (HUD):

- ☒ No
- ☐ Yes, and it includes a research component
- ☐ Yes, and it involves clinical care ONLY

4.3 * TYPE OF RESEARCH: (REQUIRED) Select the option that best fits your project (Click the orange question mark to the right for definitions and guidance):

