7.3 DESIGN: Briefly describe the study design (e.g., observational, interventional, randomized, placebo-controlled, blinded, cross-over, cross-sectional, longitudinal, pharmacokinetic, etc.):

This study will have two parallel arms. The first one will be a **double-blinded, single-institution, randomized controlled trial** of patients undergoing in-person rehabilitation following arthroscopic meniscus repair. The second will be a **single blinded, single institution, prospective clinical trial** of patients undergoing in-person or telehealth rehabilitation of orthopaedic knee conditions. In both arms, the study compare (1) a standard-of-care rehabilitation protocol versus (2) standard-of-care rehabilitation combined with BFR training with cuff occlusion applied to the affected extremity. All patients will be enrolled prospectively, prior to beginning rehabilitation. Patients with arthroscopic meniscus repair who are unable or choose not to participate in in-person rehabilitation will be allowed to undergo telehealth rehabilitation through the second arm of this study.

Rehabilitative exercises would be advanced per the physical therapists' discretion with similar exercises for patients in both groups for direct comparison. These exercises are part of an already-established rehabilitation protocols that are in place, with the only difference being the addition of the BFR cuff in the intervention group. Patients would undergo their supervised rehabilitation for 8-12 weeks.

7.4 BACKGROUND AND SIGNIFICANCE: Briefly provide the background and significance of this study (e.g. why is this study needed) (space limit: one half page):

If this is a first in humans study, please summarize the safety data from the animal studies. For pediatric drug or device studies, please identify if this is the first study in pediatric populations.

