*** Provide details about the subject identification methods: (REQUIRED)**

Subjects will be identified in the outpatient clinic setting at the UCSF Orthopaedic Institute by one of the staff surgeons/physicians. For the randomized cohort, patients will be identified after having an MRI-confirmed meniscus injury for which surgical management via repair is recommended. Participants would be identified pre-operatively at their pre-operative clinic visit via the inclusion criteria previously described. For the non-randomized cohort, surgeons /physicians will identify patients with orthopedic knee conditions being referred to UCSF physical therapy. Screening of participants for exclusion criteria would be performed by both the treating surgeon and clinical research coordinator.

10.3 * SEARCHING OF MEDICAL RECORDS: (REQUIRED)

Whose patients are they:

- ☒ Investigators' own patients or patients seen within the same practice
- ☐ Patients not under the care of the investigators

How and by whom will records be accessed and searched (check all that apply):

- ☒ Self-search in APeX or other medical records source
- ☐ Self-search using UCSF's Research Cohort Selection Tool
- ☐ CTSI Consultation Service Recruitment Services
- ☐ UCSF Academic Research Services (ARS)
- ☐ University of California Research Exchange (UC ReX)
- ☐ Other method (describe below)

10.4 DETERMINATION OF ELIGIBILITY: How, when, and by whom will eligibility for recruitment be determined:

Eligibility for recruitment will be determined at surgeon/physician clinic visit after an MRI-confirmed meniscus injury for which an arthroscopic meniscus repair surgery is recommended or prior to beginning orthopaedic physical therapy rehabilitation. Both the treating surgeon/physician and the research coordinator will confirm eligibility and that the patients meet the inclusion criteria and do not have any exclusion criteria.

10.5 * INITIATION OF CONTACT: Who initiates contact (check all that apply): (REQUIRED)

- ☒ Investigators/study team
- ☐ UCSF recruitment unit (e.g. CTSI Consultation Services)
- ☐ Potential participant
- ☐ Other (explain below)

10.6 * HOW IS CONTACT INITIATED: (check all that apply): (REQUIRED)

- ☒ In person
- ☐ Phone
- ☐ Letter / email
- ☐ Website or app
- ☐ Other (explain below)

10.7 RECRUITMENT PLAN: Based on the checkboxes you chose above, please provide a narrative describing your recruitment plan. We want to know:

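### The second cohort is meant to compare BFR with standard care, but it is not randomised, has no stated assignment rule and no planned adjustment, so it cannot support an efficacy claim across knee conditions

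*Combined protocol and SAP*

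**What the plan says.** - **Goal.** Section 4.1 asks "whether BFR is a useful rehabilitation tool across various populations with musculoskeletal knee conditions". Hypotheses 1 and 2 in 7.2 are comparative and are not limited to one cohort.
- **Design.** Section 7.3 randomises only patients having in-person rehabilitation after arthroscopic meniscus repair. The second cohort is a "single blinded, single institution, prospective clinical trial". The same section then says: "In both arms, the study compare (1) a standard-of-care rehabilitation protocol versus (2) standard-of-care rehabilitation combined with BFR training".
- **Allocation.** Section 9.1 gives the enrolment as "35 per group in the randomized control trial and an additional 35 for the non-randomized group". Section 10.2 says: "For the non-randomized cohort, surgeons /physicians will identify patients with orthopedic knee conditions being referred to UCSF physical therapy". That describes finding patients, not assigning treatment.
- **Case mix.** Section 9.7 admits knee conditions "including but not limited to knee osteoarthritis, patellofemoral pain, and status post knee arthroscopy". Section 7.3 adds a further route: "Patients with arthroscopic meniscus repair who are unable or choose not to participate in in-person rehabilitation will be allowed to undergo telehealth rehabilitation".
- **Analysis.** Section 7.13 plans a comparison of groups at alpha 0.05 with methods that do not assume normality. It names no covariates, strata or matching, and does not say whether the second cohort is analysed alone or pooled.

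**The concern.** A group comparison isolates BFR only if the groups would otherwise have fared alike. In the second cohort nothing in the plan secures that. A patient a few weeks after arthroscopy or meniscus repair is expected to change over 8 to 12 weeks whatever the treatment; a patient with long-standing osteoarthritis or patellofemoral pain may change much less. Post-operative status also brings a different programme: section 7.9 gives these patients two sessions a week while non-weightbearing, against one to two for the others, and adds electrical stimulation to BFR in that phase. If the two kinds of patient are unevenly spread between BFR and control, the comparison mixes their recovery with the effect of BFR. If there is no control arm, natural recovery is not separated from BFR at all.

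At stake is the general conclusion. Any statement about BFR beyond in-person meniscus repair would rest on this cohort alone.

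**Working it through.** **1. The plan's own figures (7.13, 9.3).** Knee extension rises 11% (SD 13) with BFR and 3% (SD 9) in control.

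- Planned effect: 11 − 3 = 8 points.
- Pooled SD: √((13² + 9²)/2) = 11.18. Effect size: 8/11.18 = 0.716, stated as 0.72.
- At 80% power, 25 per group reproduces with a one-sided alpha of 0.05 (24.6 by t-test). A two-sided test needs 32 per group. Sidedness is not stated; that is a separate matter.
- 25 × 3 = 75, and 75 × 1.40 = 105.

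The 25 patients with other knee conditions equal one group of this calculation. No two-group calculation is given for them.

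**2. Is there a control arm?** Section 7.3 says both cohorts compare the two treatments. Sections 7.13 and 9.3 count 75 as 25 per group and 105 as 35 per group, which is three groups, with the second cohort as the third. These readings conflict.

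- *All 35 receive BFR.* There is no concurrent comparison. Even on the plan's own figures, a before-after reading would credit BFR with all 11 points, although 3 of them occur without it.
- *The 35 are split.* An even split gives 17 and 18. Steps 3 to 5 take this case.

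**3. Size of the bias if split.** The documents give no recovery rates, so both inputs are assumptions.

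Spurious difference = (extra natural recovery of post-operative over chronic patients) × (post-operative share in BFR − share in control).

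| Recovery gap (points) | Share difference 0.2 | Share difference 0.4 |
|---|---|---|
| 10 | 2 | 4 |
| 20 | 4 | 8 |
| 30 | 6 | 12 |

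A 20-point gap with a 0.4 difference equals the whole planned effect. A share difference of zero gives no bias. A negative one gives the same sizes with the opposite sign, which would hide a benefit.

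**4. Chance of a false finding.** Simulation with no true BFR effect, within-condition SD 11.18, 17 against 18 patients, and a two-sided t-test as a stand-in for the unspecified test. Over the table's range, the chance of a significant result favouring BFR is 7% to 49%, against a nominal 2.5%. With post-operative status as a covariate it returns to about 2.5%.

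**5. What randomising would buy.** Two-sided t-test power at d = 0.72 is 41% with 12 against 13 evaluable patients, and 54% with 17 against 18 and no losses.

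**The case against.** The strongest reply is that the cohort is openly labelled non-randomised, that the study title concerns meniscus repair, and that the randomised comparison is untouched as long as the cohorts are not pooled. That stands, and it limits the point to claims drawn from the second cohort. It does not remove the point, because 7.3 plans a treatment comparison there and 7.2 does not exempt it from the hypotheses.

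Four stronger readings are tempting, and the documents do not support them.

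- *BFR will go mainly to post-operative patients, so the bias favours the hypothesis.* Section 4.1 does say "Patients that may benefit most from this are post-operative knee patients during early phases", but the sentence goes on to name patients with knee joint conditions who tolerate load poorly. It is also a project summary, not an instruction on allocation. The bias could run the other way: Hypothesis 1 compares force after rehabilitation, so a surplus of recently repaired knees could lower the BFR group's result. Section 7.9 also lets the uninjured leg supply the strength baseline when the injured side cannot be tested, which would make gains look smaller.
- *The clinician or the patient chooses the treatment.* Section 10.2 says only who identifies patients. The supportable statement is that no rule is given.
- *Adjustment cannot help.* For the imbalance quantified above it does, as step 4 shows. It cannot deal with unmeasured reasons for receiving BFR.
- *Randomising this cohort would settle the question.* It would remove the allocation bias, but 35 patients leave about 40% to 54% power. The documents also describe no randomisation procedure for the first cohort that could simply be extended.

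**Conclusion.** The point holds for the second cohort. The plan intends a BFR-versus-standard-care comparison there without randomisation, without a stated assignment rule, with an unclear control arm, with mixed post-operative and chronic conditions, and with no planned adjustment. Case mix and natural recovery could create or conceal an effect.

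The spurious difference is 2 to 12 points against a planned 8, if the cohort is split, if the recovery gap is 10 to 30 points, and if post-operative patients are more common under BFR by 20 to 40 percentage points. All three conditions are assumptions, and the sign depends on the last. If all 35 receive BFR, this arithmetic does not apply and natural recovery is uncontrolled.

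The randomised meniscus-repair comparison is not affected if it is analysed alone.

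**What to change.** 1. In 7.2, 7.3 and 7.13, restrict the confirmatory tests of Hypotheses 1 and 2 to the randomised meniscus-repair cohort, analysed separately.
2. Label the second cohort exploratory. State how BFR is assigned and whether there is a concurrent control, and make the group counts in 7.13, 9.1 and 9.3 agree with that.
3. Report the second cohort by diagnosis. Adjust any BFR-versus-control estimate for post-operative status and baseline strength, and make no efficacy claim across knee conditions.
4. As an option, if feasible, randomise this cohort 1:1, stratified by post-operative status. At 35 patients it would remain exploratory for lack of power.

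Items 1 to 3 are mainly changes of wording. Post-operative status can come from the clinical records that 7.9 already plans to review. The real cost is that the trial gives up a confirmatory claim beyond in-person meniscus repair. Item 4 would also need a randomisation list and consent wording, and some patients with a firm preference may decline.

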In healthy patients, there have been demonstrated benefits in knee extension torque and cross-sectional area, although inconsistencies in study protocols limit interpretation [5, 9, 10]. A randomized controlled trial has demonstrated that BFR can have benefits not just distal to the area of occlusion, but also proximally on the ipsilateral extremity and even on the contralateral extremity which may be attributable to the systemic benefits of the training [1-3, 5].

Orthopaedic studies to date have largely focused on BFR in patients undergoing anterior cruciate ligament reconstruction, as it is well-described that this group has significant quadriceps atrophy. Thus far these studies have proven to be safe and do demonstrate the possibility in reducing atrophy [5-11]. Studies, however, are limited in the population of patients undergoing arthroscopic meniscus repair and other orthopaedic knee conditions. Patients undergoing arthroscopic meniscal repair also have decreased quadriceps force production like those undergoing anterior cruciate ligament reconstructions which is exacerbated by a period of immobilization post-operatively [12,13]. Furthermore, patients with knee osteoarthritis have also been found to have increased quadriceps muscle atrophy [28]. This diminished strength contributes to poor loading mechanics, therefore increasing the risk of further injury and osteoarthritis [14, 15].

Therefore, it is of interest to pursue rehabilitative protocols aimed at improving strength in those with orthopaedic knee conditions, including arthroscopic meniscus repair, as it is important to discover if BFR can cause a clinical difference in those with perhaps less natural quadriceps atrophy than those undergoing anterior cruciate ligament surgery. One pilot study evaluated BFR after knee arthroscopy (including several heterogenous procedures) and demonstrated nearly two times increased extension strength compared to controls, hinting that benefits may not be just in those with as severe quadriceps atrophy as seen in anterior cruciate ligament injuries.

7.6 * TREATMENT PROTOCOL: Is this a treatment study, i.e. does this study intend to provide treatment to individuals with a medical or psychological condition: (REQUIRED)

☒ Yes ☐ No

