rehabilitation protocol versus (2) standard-of-care rehabilitation combined with BFR training with cuff occlusion applied to the affected extremity. All patients will be enrolled prospectively, prior to beginning rehabilitation. Patients with arthroscopic meniscus repair who are unable or choose not to participate in in-person rehabilitation will be allowed to undergo telehealth rehabilitation through the second arm of this study. Rehabilitative exercises would be advanced per the physical therapists' discretion with similar exercises for patients in both groups for direct comparison. For patients undergoing meniscus repairs, these standardized post-operative protocols will include a period of non-weightbearing followed by a period of weightbearing as guided by the surgeon. Intra-operatively, or prior to the initiation of the rehabilitation, the following will be noted to guide future analysis: Outerbridge Scale of Cartilage Injury, the type of meniscus tear, type of repair, and the percentage of meniscus resected. Clinical records would be reviewed for clinical, operative, and imaging data.

Aim 1: Evaluate the force production and strength of the affected extremity after BFR compared to those in the standard rehabilitation control group.

Hypothesis 1: *Force production, as measured by peak force determined via hand-held dynamometer at 30 and 90 degrees of knee flexion for quadriceps and hamstrings, will be significantly higher after rehabilitation with incorporation of BFR relative to patients without BFR.*

Rationale: If it is shown that BFR can improve strength and limit atrophy in patients with orthopaedic knee conditions, it will provide an avenue of rehabilitation for quicker recovery.

Approach:

The BFR protocol itself is guided by prior studies. While there has not been a consistent protocol used, several themes in the more recent studies remain constant and would be used. Tourniquet setting would be set to 80% of the extremity arterial limb occlusion pressure (LOP) recorded with the patient lying supine, which is similar to that of prior studies and therefore varies with a patient's personalized occlusion pressure [5, 11, 16].

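### The randomised cohort's criteria let in meniscus repairs done with a ligament reconstruction, and the plan neither stratifies on nor adjusts for this, so the result may not speak to the section 7.5 question and loses precision.

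*Combined protocol and SAP*

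**What the plan says.** **Eligibility.** Criterion 1 in section 9.7 covers patients "undergoing arthroscopic meniscus repair of either the medial or lateral meniscus, or both. We will include all meniscus repair types". It does not ask for an isolated repair. Section 9.8 has two exclusion bullets, "Patients will be excluded if they have risk factors for venous thromboembolism, including cancer, currently on oral contraceptive medications, or prior history of thromboembolism" and "Additional exclusion diseases include sickle cell anemia, Diabetes Mellitus, and vascular disease for increased risk for vascular complications", followed by a definition of vascular risk. None concerns another procedure at the same operation. Under section 10.2, for the randomised cohort, "patients will be identified after having an MRI-confirmed meniscus injury for which surgical management via repair is recommended"; ligament status is not screened.

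**The question.** Section 7.5 says earlier orthopaedic work on BFR was mostly done after ACL reconstruction, because "it is well-described that this group has significant quadriceps atrophy". It then gives its interest as whether BFR makes a "clinical difference in those with perhaps less natural quadriceps atrophy than those undergoing anterior cruciate ligament surgery".

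**Data and analysis.** Section 7.9 lists what is noted at or before the start of rehabilitation to guide later analysis: "Outerbridge Scale of Cartilage Injury, the type of meniscus tear, type of repair, and the percentage of meniscus resected". Concomitant ligament surgery is not on the list. The same paragraph adds that clinical records will be reviewed, including operative data. Sections 7.3 and 7.9 name no stratification factor. Section 7.13 plans a comparison of groups, with no covariate and no subgroup for this factor.

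**The concern.** Nothing in the documents says whether a repair done together with a ligament reconstruction belongs in the randomised cohort. The written criteria let it in. Section 7.5 uses ACL surgery patients as the group against which the new question is set, so admitting them blurs whom the answer is about.

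Two things are at stake. The first is the target population: the estimate would be an average over isolated and combined procedures, with weights set by whatever mix the clinics supply. A reader wanting the effect after repair in knees with less atrophy could not read it off. The second is precision: if the two types of operation recover strength differently, the difference adds to the outcome variance, and an analysis that ignores it carries that variance in full. The randomised cohort is planned at only 25 evaluable patients per arm.

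**Working it through.** **1. Is the patient eligible?** Take a patient aged 18 to 60 with an MRI-confirmed meniscus injury, repair recommended, and an ACL reconstruction planned at the same operation. Section 9.7 criterion 1: met. Section 9.8: no exclusion applies. Section 10.2: identified. Sections 7.9 and 11.5 repeat the exclusions and add nothing on ligament surgery. The patient can be randomised. This follows from the criteria as written; the plan does not state that such patients will be enrolled.

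**2. The plan's own figure (section 7.13).** Changes in knee extension torque of 11% (SD 13) and 3% (SD 9):
- pooled SD = √((13² + 9²)/2) = 11.18
- d = (11 − 3)/11.18 = 0.716, stated as 0.72
- n per group at power 0.8, alpha 0.05: 25 one-sided, 32 two-sided (t-test)

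The stated 25 per group therefore reproduces only as a one-sided test, and sidedness is not stated. That is a separate matter; both versions of power are shown below.

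**3. Effect of mixing on precision.** Let p be the share of combined procedures and D the gap in mean recovery between the two types, in units of the within-type SD. The documents give neither. Assumed: p = 0.2 to 0.6, D = 0.5 to 1.5. For illustration, 0.72 is taken as the effect size within each type, the same in both.

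SD inflation = √(1 + p(1 − p)D²)

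| p | D | SD inflation | d = 0.72 / inflation | Power at 25 per arm, one-sided | two-sided |
|---|---|---|---|---|---|
| no mixing | – | 1.00 | 0.72 | 0.81 | 0.70 |
| 0.2 | 0.5 | √1.04 = 1.02 | 0.71 | 0.79 | 0.69 |
| 0.5 | 1.0 | √1.25 = 1.12 | 0.64 | 0.73 | 0.61 |
| 0.5 | 1.5 | √1.5625 = 1.25 | 0.58 | 0.64 | 0.51 |

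p = 0.5 gives the largest inflation for a given D.

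**4. Chance imbalance is the same variance.** With 25 per arm, p = 0.5 and D = 1.5, in squared within-type SD units:
- within-type variance of the arm difference: 2/25 = 0.080
- variance from a chance difference in shares: D² × 2p(1 − p)/25 = 2.25 × 0.02 = 0.045
- total: 0.125 = 0.080 × 1.5625

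The total equals the variance with the inflated SD from step 3. Imbalance between arms is how the inflation shows itself in a single trial and must not be added on top.

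**5. Precision of an isolated-repair estimate.** Of 25 evaluable per arm, 25 × 0.8 = 20 down to 25 × 0.4 = 10 would be isolated repairs. The 95% half-width is about 1.96 × √(2/n) SD: 0.62 SD at n = 20 and 0.88 SD at n = 10, against 0.55 SD for 25 unmixed patients per arm.

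**The case against.** **A broad repair population may be intended.** The hypothesis and aims (sections 7.1 and 7.2) compare BFR with standard rehabilitation and never mention isolated repair. The contrast with ACL surgery is a background remark, hedged with the word perhaps. Section 7.5 also says quadriceps force falls after meniscal repair as it does after ACL reconstruction. This stands as a reason not to insist on exclusion. It does not settle whether combined procedures are meant to be in, or how a result from a mixed cohort would be read against section 7.5.

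**Randomisation protects the comparison.** A reader might infer that the trial cannot isolate the effect of BFR. The documents do not support that: assignment is randomised and section 7.3 gives the cuff as the only difference between arms, so the contrast is unbiased in expectation for whoever is enrolled.

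**The patients could be identified later.** A reader of the section 7.9 list might infer that combined procedures could never be separated out. The review of operative records, in the same paragraph, means they could be. Without a planned field, stratum or analysis, though, the separation would be post hoc.

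**The size rests on assumptions.** This stands. At the low end of the assumed range the effect is trivial, 0.72 to 0.71.

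**Conclusion.** The point holds as a gap in eligibility and analysis. The criteria admit repairs combined with ligament reconstruction, and the plan neither stratifies on nor adjusts for it. The result may therefore not answer the section 7.5 question, and it gives up precision that could be kept.

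The population mismatch rests on the text alone, provided such patients present. The loss of precision rests on assumption: for a 20-60% share and a 0.5-1.5 SD gap, the SD rises by about 2-25%, d falls to about 0.71-0.58, and power at 25 per arm falls from 0.81 to 0.79-0.64 one-sided, or from 0.70 to 0.69-0.51 two-sided.

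A reader might also infer that a positive result driven by ACL patients would only repeat what is known. The documents do not go that far: sections 7.1 and 7.5 describe the ACL studies as showing potential and possibility.

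**What to change.** 1. State in section 9.7 whether concomitant ligament reconstruction is eligible for the randomised cohort.
2. If it is, add concomitant ligament reconstruction (yes/no) to the intra-operative data in section 7.9.
3. Stratify the randomisation on it, using the surgical plan or, if assignment follows surgery, the operative finding.
4. In section 7.13, adjust the strength comparison for it. Since the plan calls for non-parametric methods, a stratified rank test (van Elteren) would do, with the mean difference and confidence interval from a linear model containing the factor. If the BFR effect is similar in both types, this recovers nearly all the precision lost in step 3 of the working.
5. Report the isolated-repair estimate with its confidence interval beside the overall result.

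**Cost.** One field and one stratification factor, with no loss of accrual. The isolated-repair estimate will be imprecise (step 5 of the working) and should be presented as an estimate, not as a second powered test.

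**Exclusion is optional.** These patients could join the second cohort, whose criterion is open-ended, but they would then contribute no randomised information. Section 12.4 reports 11 repairs in four weeks. With an assumed 50% consent, 70 randomised patients take 70/(11 × 0.5) ≈ 13 four-week periods. Excluding 20% gives 70/(11 × 0.8 × 0.5) ≈ 16 periods; excluding 60% gives 70/(11 × 0.4 × 0.5) ≈ 32, or 2.5 times as long. The sponsor should weigh that against a cleaner population.
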